Aim 2. To assess the feasibility and acceptability of the optimized *MeSSSSage* intervention. In Phase 2 we will evaluate the feasibility and acceptability of two intervention components using a controlled 4-arm factorial design (n=160; 40 per arm): 1) real-time mobile voice information and support group alone, 2) asynchronous/on-demand text-based group support only, and 3) real-time mobile voice information and support group plus asynchronous/on-demand text-based group support. Feasibility and acceptability will be assessed via back-end data, surveys, and IDIs with purposively selected participants (n=30) and moderators.

Aim 3. To explore the preliminary effectiveness of the optimized *MeSSSSage* intervention components on six-month maternal and neonatal health outcomes. Phase 2 data will help us develop a preliminary understanding of the impacts of the intervention components on MCH health-related knowledge, behaviors and outcomes including exclusive breastfeeding, immunization, family planning uptake, postnatal visits, mental health and empowerment; however, it is not statistically powered to formally assess effectiveness.

This study is significant and innovative in addressing key priorities of NICHD's Pregnancy and Perinatology Branch and using systematic, user-centered and experience-driven design approach. These results will inform the most acceptable, feasible, and potentially efficacious intervention design to be robustly tested through an R01 mechanism to assess effectiveness for maternal and infant health outcomes, explore other research questions relevant to intervention development and scale-up for postnatal health among South Asian women, and explore generalizability across populations.

Significance

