Phase 2: Pilot test of optimized intervention, assessment of feasibility and acceptability (Aim 2) and preliminary effectiveness on maternal and infant health outcomes (Aim 3). After analysis of Phase 1 data, *MeSSSSage* will be adapted based on participant feedback and content will be expanded to cover topics relevant to the first six months of the postnatal period. If data from Phase 1 suggest that the tested mobile group forum modalities are not appropriate for this population, we will adapt our study protocol to explore other feasible means of providing information and support (e.g., SMS or video). We anticipate developing and testing two different modalities of postnatal education and support in a factorial design with an additional control arm for a total of four different group compositions. All women, including the control group, will receive the standard of care provided by the Government of India and described above. We will conduct a pilot test of the intervention using two groups per intervention modality for a total of eight separate groups, a total of 160 women (Table 2). Exact group structure and duration will be informed by Aim 1, but we anticipate the following:

Table 2: MeSSSSage components to be tested in feasibility and acceptability assessment (Phase 2).

	Arm 1	Arm 2	Arm 3	Control
Real-time live voice call group meeting: Interactive educational program with scripted didactic component plus discussion/question. Lead and moderated by health professional.	X		X	
Text-based, asynchronous, on-demand social support: App-based small group text-based communication. Moderated by health professional.		X	X	
Standard of care: 3 visits in the first 7 days postnatal (facility and home)	X	X	X	X

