Aim 3. Preliminary effectiveness of the MeSSSSage intervention components on six-month MCH outcomes. Using the quantitative survey data, we will statistically evaluate differences by study arm in improvements in women's knowledge, behaviors, and maternal and child health outcomes, compared to the control group (including effect sizes, controlling for relevant socio-demographics as necessary). Figure 1 displays the outcomes that are theoretically related to our intervention targets. Our main *knowledge* outcome will be a composite score representing the proportion of correct answers from a series of questions on knowledge of breastfeeding, newborn and infant care, maternal and infant danger signs, newborn care, and family planning, topics that will be covered within our interactive educational group component. Our main *behavior* outcome will be self-reported exclusive breastfeeding at 6 months. Our two main health related outcomes will be: (1) completion of early childhood immunization schedule; and (2) postnatal family planning uptake. We will also measure women's social support and related mental health status (depression and anxiety) using scales that have been previously validated in similar populations such as the Hopkins Symptom Checklist⁴¹ and the Multidimensional Scale of Perceived Social Support⁴². Finally, women's empowerment will be measured using decision-making and mobility scales.^{43,44}

Sample Size. This pilot development study is not formally powered to detect significant differences in outcomes, but will give insight into directionality of changes. The per group sample size was selected based on feasibility of recruitment, intervention delivery, and the interpersonal interaction important for a group-focused intervention. The sample is sufficiently large to assess the feasibility and acceptability outcomes through descriptive statistics.

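### Phase 2 is laid out as a voice-by-text factorial, but Aim 3 specifies only arm-versus-control differences, so no stated contrast estimates a component effect from all 160 women

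*Protocol*

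**What the plan says.** Under Specific Aims, Aim 2, the protocol plans to evaluate "two intervention components using a controlled 4-arm factorial design (n=160; 40 per arm"). Under Phase 2 it expects to test "two different modalities of postnatal education and support in a factorial design with an additional control arm". Table 2 shows a complete 2x2: voice in Arms 1 and 3, text in Arms 2 and 3, neither in control, and standard of care in all four. Delivery is "using two groups per intervention modality for a total of eight separate groups, a total of 160 women".

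Under Specific Aims, Aim 3 seeks a "preliminary understanding of the impacts of the intervention components on MCH health-related knowledge, behaviors and outcomes". The matching Analysis paragraph says "we will statistically evaluate differences by study arm in improvements in" knowledge, behaviours and health outcomes, "compared to the control group (including effect sizes, controlling for relevant socio-demographics as necessary"). It names no main effect, no interaction and no model. The Sample Size paragraph disclaims formal power and says that the study "will give insight into directionality of changes". The SAP repeats that both phases were sized for feasibility, and gives analysis methods for Phase 1 only.

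**The concern.** The aim is worded in terms of components and the design is factorial, but the analysis sentence is worded in terms of arms. In a 2x2 layout every woman can inform both component effects. A comparison of one arm with control uses 80 of the 160 women and leaves the other 80 out of that estimate.

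Since direction is the only yield that the protocol promises for these outcomes, precision bears directly on whether an observed direction can be trusted and carried into the larger trial. If the contrasts are not named in advance, the analyst can also choose between arm-level and pooled estimates after seeing the results.

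**Working it through.** **Inputs from the protocol.** Four arms of 40 (Specific Aims, Aim 2); the 2x2 layout (Table 2); eight groups, two per condition (Phase 2); background exclusive breastfeeding of 50.3% in the study state (Significance).

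**Assumptions.** The documents give no SD, ICC or effect size. I use SD = 1, ICC from 0 to 0.20, and +10 percentage points for each component alone. All are illustrative.

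**1. The plan's own figure.** 4 x 40 = 160, and 160/8 = 20 women per group. The stated total is reproduced. There is no power statement to reproduce.

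**2. Precision with independent women.**
- Arm 1 or Arm 2 v control: variance 1/40 + 1/40 = 0.050; SE = 0.224 SD.
- Voice margin (Arms 1+3 v Arm 2+control) or text margin (Arms 2+3 v Arm 1+control): variance 1/80 + 1/80 = 0.025; SE = 0.158 SD.
- Variance ratio 0.050/0.025 = 2.0; SE ratio 1.41.
- Arm 3 v control: the sum of the two additive effects has variance 0.050, the same as the direct comparison. Nothing is gained.
- Interaction, (Arm 3 - Arm 2) - (Arm 1 - control): variance 4/40 = 0.100; SE = 0.316 SD.

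For exclusive breastfeeding near 50.3%, the 95% half-width is 1.96 x sqrt(2 x 0.503 x 0.497/40) = 21.9 points for an arm contrast. With 80 per side it is 15.5 points.

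**3. Clustering by delivery group.** With 20 women per group the design effect is D = 1 + 19 x ICC.
- All four arms clustered equally: D cancels and the ratio stays at 2.0.
- Three intervention arms clustered, control not: ratio = [(D+1)/40] / [(3D+1)/160] = 4(D+1)/(3D+1).
- Only the voice arms clustered: the voice ratio stays at 2.0; the text ratio = (2/40) / [(2D+2)/160] = 4/(D+1).

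| ICC (assumed) | D | Ratio, control unclustered | Text ratio, only voice arms clustered |
|---|---|---|---|
| 0.01 | 1.19 | 1.92 | 1.83 |
| 0.05 | 1.95 | 1.72 | 1.36 |
| 0.10 | 2.90 | 1.61 | 1.03 |
| 0.20 | 4.80 | 1.51 | 0.69 |

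A ratio below 1 means that the margin is the noisier estimate.

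**4. Non-additivity.** The voice margin equals (Arm 1 - control) plus half the interaction. As an estimate of the single-component effect, the margin has the smaller mean squared error while 0.025 + (interaction/2)^2 < 0.050, that is, for an interaction below 2 x sqrt(0.025) = 0.316 SD in size. That threshold equals the interaction's own SE, so the pilot cannot tell which side of it the truth lies on.

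**5. Chance of an observed sign opposite to the true one.** Take control at 50.3%, each component alone at 60.3%, independent women and a normal approximation. For Arm 1 v control, SE = sqrt[(0.503 x 0.497 + 0.603 x 0.397)/40] = 11.1 points, and the chance is Phi(-10/11.1) = 18%. For the margin, SE is half the square root of the four arm variances summed.

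| Gain in combined arm (assumed) | Margin (points) | SE (points) | Wrong-sign chance, margin | Wrong-sign chance, arm v control |
|---|---|---|---|---|
| +20 (additive) | 10 | 7.7 | 10% | 18% |
| +14 | 7 | 7.7 | 18% | 18% |
| +10 (redundant) | 5 | 7.8 | 26% | 18% |

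The advantage is gone at an interaction of -6 points (14 - 20), while the interaction's SE is about 15 points (2 x 7.7).

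**The case against.** The best defence is that arm-level contrasts answer a legitimate question. The Aim 2 analysis asks whether the combination or a single component works best, and the pilot is meant to choose a design for a larger trial. Choosing among packages rests on arm-level effects, not on effects averaged over the other component. Both components are group communication moderated by a health professional, so some redundancy is plausible, and then the margins understate what each does alone. This stands, and it is why the arm contrasts should stay.

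A reader might infer that the plan throws the factorial structure away, or that it doubles the variance of every component estimate. The documents support neither. The Aim 3 sentence names no model, and main effects can be formed from the same four arm means, so the gap is in what is specified. The factor of two needs independence or equal clustering, whereas components delivered in groups against a standard-of-care control make unequal clustering plausible. Clustering in the voice arms alone is the least favourable case for text. Table 2 describes the text component as moderated small-group communication, so clustering there is plausible too, but the documents give no ICC to settle it.

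It is also fair to say that the Phase 2 text is provisional: group structure awaits Phase 1, and the Timeline schedules preparation and ethics modifications before Phase 2 starts. That lowers the urgency but also makes this a convenient time to name the contrasts.

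**Conclusion.** The concern holds as a gap in specification. The design and the wording of Aim 3 call for component effects, and no stated contrast estimates one from all 160 women. Naming the margins would halve the variance of the voice and text estimates under independence or equal clustering. The gain is smaller if only the intervention arms cluster, and uncertain for text if clustering is confined to the voice arms. Reading a margin as a single-component effect further requires approximate additivity, which 40 women per cell can check only weakly.

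Two stronger conclusions might be drawn, and neither is supported. Arm-versus-control comparison is not an error, since it estimates a different and useful quantity. Nor does the finding upset any power or sample-size claim, because both documents say that the study was not sized for power. The point is a modest, inexpensive improvement to a pilot analysis.

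**What to change.** In the Phase 2 analysis text, for each of the four main Aim 3 outcomes (knowledge score, exclusive breastfeeding, immunization, family planning):

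- Keep the three arm-versus-control differences.
- Add the voice main effect (Arms 1+3 v Arm 2+control) and the text main effect (Arms 2+3 v Arm 1+control), each with a 95% CI.
- Estimate these from an additive model or with +/-1 effect coding (the main effect is then twice the coefficient). Ordinary 0/1 indicators with a product term return Arm 1 v control and Arm 2 v control, at SE 0.224 SD, and gain nothing.
- Report the voice-by-text interaction with its CI (SE about 0.32 SD under independence). State the outcome scale, and that the margins equal single-component effects only if the components act roughly additively on that scale.
- Allow for the delivery groups. Eight groups will estimate an ICC poorly, so show the intervals over a stated range of ICC values as well.

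The cost is about a paragraph of wording and no new data. The downsides are small: each main effect is an average over the other component, additivity cannot be checked well, and the estimates for the main outcomes rise from 4 x 3 = 12 to 4 x 6 = 24, all to be read as descriptive.

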Procedures: Unless found not feasible or acceptable within Phase 1 activities, women will be recruited using the approach described above (Aim 1). At the time of enrollment, the study protocol will be described to the women following informed consent procedures and written informed consent will be obtained from interested women, and their phone numbers will be collected (and tested). Women who do not have a phone will be provided with a phone and all participants' airtime will be covered for the length of the six-month research project. If they consent to participate, women will be randomly enrolled into one of the three study arms, or control, using a random number generator. We will test each study condition using two groups of women, with intervention initiation staggered one month apart. Women in the control group will receive the standard of care for women in this population. All women will be given 50 Indian Rupees for participation in each session (in addition to airtime and phone if needed), and ASHAs will receive 150 Indian Rupees for moderating each session. Assessment of feasibility and acceptability (Aim 2) and preliminary effectiveness (Aim 3) will be accomplished using a mixed-methods approach that will include quantitative surveys, in-depth interviews, and technology assessment.

Survey data collection: At study enrollment, a baseline survey will be administered by a research assistant in the respondent's home. Roughly six months postnatal, after having the opportunity to participate in approximately 24 MeSSSSage sessions (final number to be determined in Phase 1 activities), women will be visited in their homes for the endline survey. We will also capture women's health record cards and ASHA registers to validate self-reported health outcome data. Data will be collected on a tablet using REDCap mobile research administration software (a highly secure platform), stored in a password protected database at UCSF, and no identifiable information will be included with the data (names, phone numbers, and addresses will be stored separately and linked by an ID).

In-depth interviews: Additionally, in-depth interviews (IDIs) will be conducted with a selection of 10 women from each intervention condition (30 IDIs), purposively sampled based on high/low participation rates determined by the end line survey. We will collect data on experiences with MeSSSSage and how to improve it.

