Technology assessment: Finally, we will collect and analyze the quantitative backend data from the prototype to gain more insight into women's participation in the intervention, including attendance and level of participation in group interactive educational sessions, use of mobile social support platform (number of posts, frequency, topic), etc. Text data from transcripts of the educational sessions and content of group messaging will be analyzed for content in order to understand primary educational needs and interests for postnatal women.

Group moderator survey and interview: ASHA facilitators moderating the groups will be asked to respond to a short questionnaire after each group session to understand: preparation and delivery time, content, efficiency, acceptability and satisfaction with the group model, perspectives of impact, challenges, and any follow-up/referral necessary.⁴⁰ Regarding facilitation of groups that receive the text-based messaging intervention component only, ASHA facilitators will report on experiences in the prior week. We will also conduct monthly semi-structured interviews with each of the ASHA facilitators to understand their own preferences around the group components, their experiences preparing for and conducting the sessions, and their perspectives on mobile provision of education, care, and support.

Measures: The baseline survey content will include sociodemographic characteristics and knowledge about maternal and infant health, self-efficacy, and perceived social norms regarding MCH-related health promoting behaviors. The endline survey will include acceptability questions such as women's satisfaction with and perceptions of MeSSSSage, maternal and infant knowledge-, behavior-, and health-related questions including about breastfeeding, complementary food introduction, immunization, family planning uptake, maternal physical and mental health, etc. which have previously been used in this setting (Table 3)⁴.

Table 3: Participant survey measures (Phase 2)

Category	Measures
Sociodemographic characteristics	Age, age at marriage, educational attainment, caste, language spoken, household assets, women's status/decision-making, social support and relationship quality.
Health-related knowledge (effectiveness)	Knowledge on maternal and neonatal danger signs, best practices for infant care, family planning.

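### Aim 3 does not fix whether knowledge is analysed as change or as endline score, and leaves the baseline knowledge score unused; adjusting for it is a free, modest gain

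*Protocol*

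**What the plan says.** In the Protocol's Analysis section, Aim 3 will evaluate "differences by study arm in improvements in women's knowledge, behaviors, and maternal and child health outcomes, compared to the control group", "controlling for relevant socio-demographics as necessary". No model is named. The main knowledge outcome is a "composite score representing the proportion of correct answers from a series of questions". The other three main outcomes are exclusive breastfeeding at six months, completed early immunisation, and uptake of postnatal family planning. The Sample Size paragraph says the pilot is not formally powered but "will give insight into directionality of changes".

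Baseline knowledge is already planned. Under Measures: "The baseline survey content will include sociodemographic characteristics and knowledge about maternal and infant health". Under Survey data collection: "At study enrollment, a baseline survey will be administered by a research assistant". Knowledge is asked again at endline.

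Table 3 gives knowledge its own row ("Knowledge on maternal and neonatal danger signs, best practices for infant care, family planning"), apart from the socio-demographic row. The covariate clause therefore does not reach it as written. Table 3 does place "women's status/decision-making, social support and relationship quality" in the socio-demographic row, so the clause can already cover those, though only where judged necessary.

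The SAP gives analysis for Phase 1 only and has no Aim 3 model.

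**The concern.** The word *improvements* leans towards change from baseline but cannot settle the matter. The same clause covers breastfeeding, immunisation and family planning, which have no baseline in women recruited late in a first pregnancy. An analyst could choose a change score or an endline comparison after seeing the data, and both would fit the text.

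The choice affects precision. A plain change score is noisier than endline alone when the baseline-endline correlation is low. Endline alone discards information when the correlation is high. Since the stated purpose is to learn the direction of effects from 40 women per arm, the chance of an estimate with the wrong sign is a fair yardstick. Knowledge is the only one of the four main outcomes with a baseline measure, so it is the one that adjustment for its own baseline can help.

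**Working it through.** **Inputs from the Protocol.** Four arms of 40, 160 women in all (Specific Aims, Aim 2); eight groups, two per condition (Phase 2 text and Procedures). There is no power-based figure to reproduce. The counts agree: 4 × 40 = 160 and 160 / 8 = 20 per group.

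**Assumed, because the documents give no values.** Baseline-endline correlation r = 0.3, 0.5, 0.7; SD ratio k (baseline SD / endline SD) = 1, with 0.7 and 1.3 as alternatives; true effect 0.3 SD; intraclass correlation (ICC) 0, 0.05, 0.10; all 40 per arm analysed.

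**Step 1: variance per woman, endline SD = 1.**
- Change score: 1 + k² − 2rk
- Endline only: 1
- Endline adjusted for baseline: 1 − r²

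Change minus adjusted is (k − r)², which is never negative and is zero when k = r. Endline minus adjusted is r².

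**Step 2: precision with k = 1 and no group effect.** SE = √(V × 2/40); half-width = 1.96 × SE; wrong-sign probability = Φ(−0.3/SE). For example, adjusted at r = 0.5: SE = √(0.75 × 0.05) = 0.194 and half-width 0.38.

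| | r = 0.3 | r = 0.5 | r = 0.7 |
|---|---|---|---|
| Variance: change / endline / adjusted | 1.40 / 1 / 0.91 | 1.00 / 1 / 0.75 | 0.60 / 1 / 0.51 |
| Reduction v change | 35% | 25% | 15% |
| Reduction v endline only | 9% | 25% | 49% |
| 95% half-width (SD): change / endline / adjusted | 0.52 / 0.44 / 0.42 | 0.44 / 0.44 / 0.38 | 0.34 / 0.44 / 0.31 |
| Wrong sign: change / endline / adjusted | 12.8% / 9.0% / 8.0% | 9.0% / 9.0% / 6.1% | 4.2% / 9.0% / 3.0% |

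The reduction against change depends on k: 15%, 5%, 0% at k = 0.7, and 52%, 46%, 41% at k = 1.3. The reduction against endline only does not.

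**Step 3: shared group effect at endline, two groups of 20, k = 1.** The variance of an arm-versus-control difference is
- controls ungrouped: ICC/2 + (V − ICC)/40 + V/40
- controls also in two groups: 2 × [ICC/2 + (V − ICC)/40]

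At ICC 0.05, r = 0.5, controls ungrouped: adjusted 0.025 + 0.0175 + 0.01875 = 0.06125; endline only 0.025 + 0.02375 + 0.025 = 0.07375; reduction 17%. The adjusted half-width is 1.96 × √0.06125 = 0.49 SD. With grouped controls it is 1.96 × √0.085 = 0.57 SD.

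| ICC, controls | Reduction v change (r = 0.3, 0.5, 0.7) | Reduction v endline only | Fall in wrong-sign probability, both comparators (points) |
|---|---|---|---|
| 0.05, ungrouped | 26%, 17%, 8% | 6%, 17%, 33% | 0.8 to 4.6 |
| 0.05, grouped | 21%, 13%, 6% | 5%, 13%, 25% | 0.6 to 3.5 |
| 0.10, ungrouped | 21%, 13%, 6% | 5%, 13%, 25% | 0.6 to 3.5 |
| 0.10, grouped | 15%, 9%, 4% | 3%, 9%, 17% | 0.4 to 2.2 |

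**Step 4: cost.** One slope costs about 1/(160 − 4 − 2) = 1/154 = 0.65% of variance. Against endline only this is recovered by about r = 0.1, where 0.99 × 1.0065 = 0.996.

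**Dropout.** No rate is stated. With an assumed 20% loss and no group effect, the half-widths at r = 0.5 widen from 0.44 to 0.49 (endline only) and from 0.38 to 0.42 (adjusted). The proportional gain is unchanged.

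**The case against.** The strongest reply concerns scope. Both documents are titled Phase 1, the Protocol describes Phase 2 as anticipated and open to adaptation, and its Timeline schedules Phase 2 tool development and ethics modifications after Phase 1. A covariate list for a later, unpowered aim need not be final now. This lowers the importance. It does not remove the point, because the Protocol paragraph is the current Aim 3 analysis text.

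The second reply is that adjustment on its own would overstate precision. Women meet in groups, and an interval that ignores this would be too narrow: at ICC 0.05 and r = 0.5 the half-width is 0.49 to 0.57 SD, not 0.38. This stands, and the fix has to deal with grouping.

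Three stronger readings are tempting and are not supported.
- *The planned analysis is wrong, or rules out baseline adjustment.* Nothing in the text excludes adjustment; the wording is ambiguous.
- *Baseline and endline items will differ because content is expanded after Phase 1.* That expansion concerns the intervention and comes before Phase 2. Both surveys are Phase 2 instruments, and Table 3 has one knowledge category for them. The documents do not say that the items match, but they give no reason to expect a mismatch.
- *The wrong-sign probability falls by up to 6 points in general.* That figure needs r = 0.7, no group effect and an endline-only comparator, which is the reading the word *improvements* favours less.

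**Conclusion.** The point holds as a low-importance, no-cost improvement. The Protocol leaves the form of the knowledge analysis open and does not use a baseline score it will already have. Endline knowledge adjusted for baseline is at least as precise as either alternative, apart from the 0.65% slope cost.

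The gain is modest and uncertain. For an assumed 0.3 SD effect and equal SDs, the wrong-sign probability falls by about 1 to 6 points with no group effect, and by about 0.4 to 4.6 points at ICC 0.05 to 0.10. There is no gain over a change score if the baseline SD equals r times the endline SD. The documents supply only the sample size and the grouping; r, the SD ratio, the ICC and the effect size are assumptions.

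**What to change.** In the Phase 2 analysis text, state that:
1. endline knowledge is compared between the four arms in one model, with the baseline knowledge score as a pre-specified covariate;
2. the baseline survey is completed before allocation, since the Protocol places it at enrolment without ordering it against randomisation;
3. arm-versus-control differences are reported with 95% confidence intervals that allow for group membership, or are labelled as ignoring it. With two groups per arm the between-group variance will be poorly estimated, so the label is an honest alternative;
4. exclusive breastfeeding, immunisation and family planning uptake, which have no baseline, are compared on endline status.

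The cost is wording and one estimated slope. It needs no new data, visits or participants, and the Timeline already provides a point before Phase 2 at which to add it.
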